6.14.2.1.2. Adverse Events Related to Injection Sites

Adverse events related to injection sites will be defined using terms from the MedDRA High Level Term “Injection Site Reactions”.

The number and percentage of patients with TEAEs, SAEs, and AEs resulting in study drug discontinuation will be summarized by treatment group using MedDRA PTs. Events will be ordered by decreasing frequency. Events will be ordered by decreasing frequency.

The number and percentage of patients with TEAEs related to injection sites by maximum severity will be summarized by treatment groups using MedDRA PT.

The number and percentage of patients with TEAEs related to injection sites by timing will be summarized using MedDRA preferred terms ordered by decreasing frequency.

6.14.2.1.3. Upper Respiratory Tract Infections

Upper respiratory tract infections will be defined using all the PTs from the 2 high level terms of “upper respiratory tract infections” and “upper respiratory tract infections NEC” as defined in MedDRA.

The number and percentage of patients with TEAEs, SAEs, and AEs resulting in study drug discontinuation will be summarized by treatment group using MedDRA PTs. Events will be ordered by decreasing frequency.

The number and percentage of patients with TEAEs of upper respiratory tract infections by maximum severity will be summarized by treatment groups using MedDRA PT.

6.14.3. Clinical Laboratory Evaluation

The incidence rates of patients with treatment-emergent abnormal high or low laboratory values based on Covance reference ranges at any time postbaseline will be assessed using Fisher’s exact test for each laboratory test for SP III.

Patients will be defined as having a treatment-emergent low value if they have all normal or high values at baseline, followed by a value below the lower reference limit at any postbaseline visit. Patients with all normal or high values at baseline (no low values) will be included in the analysis of treatment-emergent low laboratory values. Patients will be defined as having a treatment-emergent high value if they have all normal or low values at baseline, followed by a value above the upper reference limit at any postbaseline visit. Patients with all normal or low values at baseline (no high values) will be included in the analysis of treatment-emergent high laboratory values.

For analytes simply classified as normal or abnormal, patients will be defined as having a treatment-emergent abnormal value if they have all normal values at baseline, followed by an abnormal value at any postbaseline visit. Patients with all normal values at baseline will be included in the analysis of treatment-emergent abnormal laboratory values.

The incidence of patients with the following elevations in hepatic laboratory tests at any time postbaseline will also be summarized. Comparison between treatment groups will be done for SP III using Fisher’s exact test.

- The percentages of patients with an alanine aminotransferase (ALT) or aspartate aminotransferase (AST) measurement greater than or equal to 3 times (3×), 5 times (5×), and 10 times (10×) the Covance upper limit of normal (ULN) during the treatment period will be summarized for all patients with a postbaseline value.
- The percentages of patients with an Alkaline phosphatase (ALP) greater than or equal to 2 times (2×) the Covance ULN during the treatment period will be summarized for all patients with a postbaseline value.
- The percentages of patients with a total bilirubin (TBIL) measurement greater than or equal to 2 times (2×) ULN during the treatment period will be summarized for all patients with a postbaseline value.

Hy's law is defined as the combination of drug related elevation of $ALT \geq 3 \times ULN$ and $TBIL \geq 2 \times ULN$, in the absence of significant cholestasis (that is $ALP < 2 \times ULN$), and in the absence of other causes of liver injury.

The analysis of elevation in ALT, AST, ALP, and TBIL will contain 3 subsets:

- patients whose non-missing maximum baseline value is less than or equal to $1 \times ULN$ for ALT, AST, ALP, and TBIL.
- patients whose non-missing maximum baseline value is greater than $1 \times ULN$ for ALT, AST, ALP, and TBIL, at the same time less than or equal to $2 \times ULN$ for ALT and AST, $1.5 \times ULN$ for ALP and TBIL.
- patients whose non-missing maximum baseline value is greater than $2 \times ULN$ for ALT and AST, $1.5 \times ULN$ for ALP and TBIL.

6.14.4. Vital Signs and Weight

Vital signs collected during the study include systolic and diastolic blood pressure (SBP and DBP), pulse, and temperature. Blood pressure and pulse measurements will be taken when the patient is in a sitting position.

The number and percent of patients meeting criteria for categorical changes of interest in vital signs and weight at any time during study will be summarized. Treatment group comparisons will be performed using Fisher's exact test.

[Table CGAX. 6.3](#) displays the criteria for categorical changes of interest in vital signs and weight. The last column of the table displays the patient populations defined by baseline categories.

The criteria to identify patients with treatment-emergent abnormal changes generally consist of a combination of two parts, an absolute threshold and a change from baseline amount.

- The absolute threshold in the criteria is based on 1) minimum postbaseline when the direction is low; 2) maximum postbaseline when the direction is high.
- The change from baseline amount in the criteria is 1) decrease from baseline (defined below and in [Table CGAX. 6.1](#)) to minimum postbaseline when the direction is low;

2) increase from baseline (defined below and in [Table CGAX. 6.1](#)) to maximum postbaseline when the direction is high.

The baseline for SBP, DBP, and pulse is defined as the last non-missing baseline value during the baseline period (See [Table CGAX. 6.1](#)). To be exact,

- For analyses including double-blind treatment phase, the baseline for SBP, DBP, and pulse is defined as the last non-missing value before randomization. The rationale for using the last available value in the baseline period is to minimize the potential confound of discontinuing or dose stabilization of medications that modulate BP and pulse during the screening phase (which is early in the baseline period).
- Similarly, for GMB-treated time, the baseline is defined as the last non-missing value before patient's first dose of GMB. This baseline definition was chosen to be consistent with the analysis approach for double-blind treatment phase as described above.

This baseline definition for SBP, DBP, and pulse applies to all analyses (both continuous and categorical) for SBP, DBP, and pulse.

The baseline and postbaseline values for temperature and weight are defined in [Table CGAX. 6.1](#).

- For continuous analyses of temperature and weight, last non-missing baseline during the baseline period will be used as the baseline.
- For the analyses of categorical changes of interest in temperature and weight,
 - the baseline is defined as the minimum value during baseline period when the direction is low.
 - the baseline is defined as the maximum value during the baseline period when the direction is high.

Table CGAX. 6.3 Criteria for Categorical Changes of Interest in Vital Signs and Weight

Parameter	Direction	Criteria	Patients Population defined by Baseline Categories
Systolic BP (mm Hg) (sitting)	Low	≤ 90 and decrease ≥ 20	All patients; >90 ; ≤ 90
	High	≥ 140 and increase ≥ 20	All patients; <140 ; ≥ 140
	PCS High	≥ 180 and increase ≥ 20	All Patients; <180 ; ≥ 180
	Sustained Elevation	≥ 140 and increase ≥ 20 at 2 consecutive visits	All patients; < 140 ; ≥ 140
Diastolic BP (mm Hg) (sitting)	Low	≤ 50 and decrease ≥ 10	All patients; >50 ; ≤ 50
	High	≥ 90 and increase ≥ 10	All patients; <90 ; ≥ 90
	PCS High	≥ 105 and increase ≥ 15	All Patients; <105 ; ≥ 105
	Sustained Elevation	≥ 90 and increase ≥ 10 at 2 consecutive visits	All patients; < 90 ; ≥ 90
Systolic BP or Diastolic BP (mm Hg) (sitting)	Sustained Elevation	Meeting criteria for systolic BP for 2 consecutive visits or meeting criteria for diastolic BP for 2 consecutive visits or both	All Patients
Pulse (bpm) (sitting)	Low	<50 and decrease ≥ 15	All patients; ≥ 50 ; <50
	High	>100 and increase ≥ 15	All patients; ≤ 100 ; >100
	Sustained Elevation	>100 and increase ≥ 15 at 2 consecutive visits	All patients; ≤ 100 ; >100
Weight (kg)	Low	(Loss) decrease $\geq 7\%$	All patients
	High	(Gain) increase $\geq 7\%$	All patients
Temperature ($^{\circ}$ F)	Low	$<96^{\circ}$ F and decrease $\geq 2^{\circ}$ F	$\geq 96^{\circ}$ F
	High	$\geq 101^{\circ}$ F and increase $\geq 2^{\circ}$ F	$<101^{\circ}$ F

Abbreviations: BP = blood pressure; bpm = beats per minute; F = degrees Fahrenheit; kg = kilograms; mm Hg = millimeters of mercury; PCS= Potentially Clinically Significant.

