## 2. Schedule of Activities

**Table CGAX.1. Schedule of Activities  
Protocol I5Q-MC-CGAX (Double-Blind Treatment Phase)**

Study Period (SP)	SP I- Screening	SP II- Prospective Baseline	SP III Double-Blind Treatment				
			30-45	14	16	30	30
(Target) Interval (days) since previous visit							
Allowable range (days) between visits	3-45	30-40 a					
Interval allowance (days)				+/- 5	+/- 2	+/- 2	+/- 2
Visit	1	2	3	4 b	5 l	6	7
Month			0	0.5	1	2	3
Assessments and Procedures							
Informed consent	X						
Inclusion/exclusion	X	X	X				
Demographics	X						
Physical examination	X						
Neurological examination c	X						X
Height	X						
Weight	X						X
Medical history	X						
Prespecified migraine history d			X				
ECG e	X		X				X
Vital signs f	X		X		X	X	X
Adverse events	X	X	X	X	X	X	X
Concomitant medications	X	X	X	X	X	X	X
ePRO and headache medication log training		X					
ePRO diary daily patient entries		X	X	X	X	X	X
Headache medication log		X	X	X	X	X	X

Schedule of Activities

Protocol I5Q-MC-CGAX (Double-Blind Treatment Phase)

Study Period (SP)	SP I- Screening	SP II- Prospective Baseline	SP III Double-Blind Treatment				
			30-45	14	16	30	30
(Target) Interval (days) since previous visit							
Allowable range (days) between visits	3-45	30-40 a					
Interval allowance (days)				+/- 5	+/- 2	+/- 2	+/- 2
Visit	1	2	3	4 b	5 l	6	7
Month			0	0.5	1	2	3
Clinical Laboratory Tests and Sampling Schedules							
Hematology	X		X				X
Clinical chemistry	X		X				X
HbA1c			X				X
Urinalysis	X		X				X
Serum Pregnancy (for women of childbearing potential) or FSH at Visit 1 (all other female patients) g	X						
Urine pregnancy g			X		X	X	X
Immunogenicity h			X		X		X
PK blood sample h					X		X
Study drug administered i			X		X	X	X j
Scales, Questionnaires, and Outcome Measures							
MIDAS			X				X
MSQ v2.1			X		X	X	X
MIBS-4			X		X	X	X
PGI-S			X				X
GAD-7			X				X
PHQ-9			X				X

Schedule of Activities, Protocol I5Q-MC-CGAX (Open-Label and Post-Treatment Phases)

Study Period (SP)	SP IV Open-Label			SP V Post-treatment		ET K
	(Target) Interval (days) since previous visit	30	30	30	60	
Interval allowance (days)	+/- 2	+/- 2	+/- 2	+/- 5	+/- 5	
Visit	8	9	10	11 b	12	
Month	4	5	6	8	10	
Assessments and Procedures						
Weight			X		X	X

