**Schedule of Activities, Protocol I5Q-MC-CGAX**

Abbreviations: AE = adverse event; ECG = electrocardiogram; ePRO = electronic patient reported outcomes; ET = early termination; FSH = follicle stimulating hormone; GAD-7 = 7-item Generalized Anxiety Disorder Scale; HbA1c = glycosylated hemoglobin; MIBS = Migraine Interictal Burden Scale; MIDAS = Migraine Disability Assessment test; MSQ (v2.1) = Migraine Specific Quality-of-Life Questionnaire; PGI-S = Patient Global Impression of Severity; PHQ-9 = Patient Health Questionnaire-9; PK = pharmacokinetics; SP = study period.

Note: Selected tests may be obtained in the event of a treatment-emergent hepatic abnormality and may be required in follow-up with patients in consultation with the Lilly Medical representative. See [Appendix 4](#) for more details regarding specific hepatic monitoring tests. If the patient has discontinued the trial and returns for hepatic follow-up, the site should collect safety data via case report form as the visit designation.

- a The eligibility period of the prospective baseline assessment will last from 30 to 40 days. Investigators and patients may have up to an additional 5 days to schedule their Visit 3 appointment (beyond the 40 days); however, eligibility will be based on the 30- to 40-day period.
- b Visit would be a virtual visit through telephone. The main purpose of telephone visits is to check any spontaneously reported AEs, concomitant medications, and performance of electronic patient-reported outcomes (ePRO) diary entries. Telephone visits can also be conducted as office visits at the study site, if more practical.
- c A neurological exam will be conducted at screening, Month 3, the final visit of the open-label period, as well as at the final visit of the post-treatment follow-up period or early termination visit in order to assess for any signs of preexisting or treatment-emergent neurological abnormalities such as stroke or other cerebrovascular events.
- d Questions about “menstrually related migraine” and “migraine with or without aura” will be included in case report form (CRF).
- e Electrocardiograms will be performed at the scheduled visits. Note: Electrocardiograms should be collected prior to blood draws and dosing. Patients must be supine for approximately 5 to 10 minutes before ECG collection and remain supine but awake during ECG collection.

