**Figure CGAX.1. Illustration of study design for Clinical Protocol I5Q-MC-CGAX.**

**Study Period I:** The study and potential risks will be explained to the patient at Visit 1. The informed consent form (ICF) must be signed before any study procedures are performed. Patients are required to discontinue all excluded medications or migraine prevention treatments at least 28 days prior to Visit 2. Botulinum toxin A or B in the head or neck area must be discontinued at least 4 months prior to Visit 2.

The screening visit (Visit 1) will consist of a full clinical assessment, including a comprehensive medical evaluation documenting medical history, and a physical and neurological examination (Section 2). Visit 1 will be completed when the last scheduled procedure of the screening assessment is completed.

**Study Period II:** Qualified patients will enter Study Period II (prospective baseline) to determine their eligibility for the study and to establish baseline data for comparison of endpoints during the treatment period. Beginning at Visit 2, patients will log in daily to the electronic patient-reported outcomes (ePRO) system to answer questions about the occurrence of headaches, headache duration, headache features, severity of headache, and use of headache medication, etc. Patients will also record the name, dose, and date of any acute headache medication on a headache medication log which will be returned to site staff at each study visit. At the end of the prospective baseline period, sites will be notified whether their patients met criteria and are eligible to be randomized at Visit 3.

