Study Period III			
Efficacy analyses (repeated measures) or average of observed monthly values	ITT population with a baseline and at least 1 postbaseline observation	Visit 3	All scheduled visits 3 < Visits ≤ 7
Efficacy analyses at LOCF endpoint		Visit 3	Last of Visit 3.01–7
Health outcome analyses (repeated measures)		Visit 3	All scheduled visits 3 < Visits ≤ 7
Health outcome analyses at LOCF endpoint or for average of observed monthly values		Visit 3	Last of Visit 3.01–7
Treatment-emergent adverse events	Safety population	All Visits 1–3*a	All Visits 3.01–7
Serious adverse events, discontinuations due to adverse events	Safety population	NA	All Visits 3.01–7
Treatment-emergent abnormal laboratory values	Safety population with normal (with respect to direction being analyzed) laboratory values at all non-missing baseline visits and who have at least 1 postbaseline observation	Low: Min of Visits 1–3 High: Max of Visits 1–3 Abnormal: All Visits 1–3	Low: Min of Visits 3.01–7 High: Max of Visits 3.01–7 Abnormal: All Visits 3.01–7
Treatment-emergent changes in temperature and weight	Safety population with a baseline and at least 1 postbaseline observation	Low: Min of Visits 1–3 High: Max of Visits 1–3	Low: Min of Visits 3.01–7 High: Max of Visits 3.01–7
Treatment-emergent changes in blood pressures, pulse, and ECGs	Safety population with a baseline and at least 1 postbaseline observation	Low: Last of Visits 1–3 High: Last of Visits 1–3	Low: Min of Visits 3.01–7 High: Max of Visits 3.01–7
Treatment-emergent immunogenicity	Safety population with a baseline and at least 1 postbaseline observation	Visit 3	All Visits 3.01–7
Continuous safety analyses (repeated measures)	Safety population with a baseline and at least 1 postbaseline observation	Last of Visits 1–3	All scheduled visits 3 < Visits ≤ 7
Continuous safety analyses – change from baseline to LOCF endpoint (ANCOVA)	Safety population with a baseline and at least 1 postbaseline observation	Last of Visits 1–3	Last of Visits 3.01–7

Patient Population with Baseline and Postbaseline Definitions by Study Period and Type of Analysis

Study Period/Analysis	Patient Population	Baseline Observation	Postbaseline Observation(s)
Study Period IV			
Maintenance of 50% Response	Open-label treatment population – GMB-treated patients with 50% response at month 3	Visit 3	All scheduled visits 7 < Visits ≤10
Treatment-emergent adverse events	Open-label treatment population	All Visits 1–7*a	All Visits 7.01–10

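### The only scheduled pre-dose weight is at Visit 1, 33 to 90 days before the first injection, so treatment-emergent weight change includes pre-treatment change

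*SAP*

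**What the plan says.** **Schedule.** Protocol Section 2 (Table CGAX.1) marks weight at Visit 1 and Visit 7 in the double-blind part, and at Visit 10, Visit 12 and early termination afterwards. Vital signs are marked at Visits 1, 3, 5, 6 and 7, and ECG at Visits 1, 3 and 7. The visit windows before dosing read "Allowable range (days) between visits 3-45 30-40", and footnote a allows five further days to book Visit 3. Visit procedures come before the injection (footnote i).

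**Weight baseline.** SAP Table CGAX. 6.1, row "Treatment-emergent changes in temperature and weight", takes the minimum (for loss) or maximum (for gain) of Visits 1 to 3 in Study Period III. SAP 6.14.4 adds: "For continuous analyses of temperature and weight, last non-missing baseline during the baseline period will be used as the baseline". The criterion in Table CGAX. 6.3 is a loss or gain of at least 7%, in all patients.

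**Galcanezumab-treated time.** The same table uses Visits 1 to 3 for patients randomized to galcanezumab and Visits 1 to 7 for placebo patients who switch. Follow-up runs through Visit 10 for both.

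**Other measures.** For blood pressure, pulse and ECG, SAP 6.14.4 and 6.14.5 take the last non-missing value before randomization. The reason given for blood pressure and pulse is to "minimize the potential confound of discontinuing or dose stabilization of medications that modulate BP and pulse during the screening phase".

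**The concern.** The minimum, maximum and last-value rules all suppose that more than one pre-dose value can exist. For temperature that is so, because it belongs to the vital signs taken at Visits 1 and 3. For weight only one value is scheduled, so all three rules return the screening weight. A patient whose weight changed by 7% between screening and the first injection would be counted as having a treatment-emergent change.

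Weight is a named secondary safety measure, and its 7% rates will be read as absolute rates as well as compared between arms. The comparison in Study Period III is protected by randomization. The galcanezumab-treated-time table has no control group, and it would pool patients whose baseline precedes the first galcanezumab dose by weeks or months with switchers whose baseline includes a weight from the day of that dose.

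**Working it through.** The documents give no figure for weight variability, so there is no plan figure to reproduce. The timing follows from the documents. The rates are an illustration on a stated assumption.

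**Step 1: gap from the only pre-dose weight to the first dose.** Visit 1 to Visit 2 is 3 to 45 days. Visit 2 to Visit 3 is 30 to 40 days plus up to 5.
- Shortest: 3 + 30 = 33 days.
- Longest: 45 + 40 + 5 = 90 days.

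**Step 2: pre-treatment share of the measured interval.** Visit 3 to Visit 7 is 14 + 16 + 30 + 30 = 90 days at target. Visit 10 is a further 30 + 30 + 30 days on, so 180 days after Visit 3.
- To Visit 7: 33/(33 + 90) = 27% to 90/(90 + 90) = 50%.
- To Visit 10: 33/(33 + 180) = 15% to 90/(90 + 180) = 33%.

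With the 2-day allowances at Visits 5, 6 and 7, Visit 3 to Visit 7 is 84 to 96 days and the share to Visit 7 is 26% to 52%.

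**Step 3: illustrative rates with no drug effect.** Assume that percentage weight change is normal with mean zero and independent increments, with standard deviation SD over 90 days. Then P(gain of at least 7%) = 1 − Φ(7/s), where s = SD × √(days since baseline/90). By symmetry the same holds for loss.

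At Visit 7:

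| SD per 90 days | Visit 3 baseline | Visit 1 baseline, 33 days earlier | Visit 1 baseline, 90 days earlier |
|---|---|---|---|
| 2% | 0.02% | 0.14% | 0.67% |
| 3% | 0.98% | 2.30% | 4.95% |
| 4% | 4.01% | 6.72% | 10.80% |
| 5% | 8.08% | 11.55% | 16.11% |

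At SD 3%, if all 243 patients in an arm had a Visit 7 weight, that is 243 × 0.0098 = 2.4 expected patients from a Visit 3 baseline, against 243 × 0.0230 = 5.6 to 243 × 0.0495 = 12.0 from Visit 1.

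At Visit 10:

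| SD per 90 days | Visit 3 baseline | 33 days earlier | 90 days earlier |
|---|---|---|---|
| 2% | 0.67% | 1.15% | 2.17% |
| 3% | 4.95% | 6.47% | 8.90% |
| 4% | 10.80% | 12.77% | 15.62% |

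At SD 3% the Visit 10 inflation is 6.47/4.95 = 1.3-fold to 8.90/4.95 = 1.8-fold. These are single-visit rates. The galcanezumab-treated-time criterion takes the extreme over all post-dose weights, so it would run somewhat higher from either baseline.

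**Step 4: effect on the Study Period III comparison.** Add an assumed mean gain on drug to the same model at SD 3%, using Fisher's exact test with 243 per arm.

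| Mean gain on drug | Baseline | Placebo | Drug | Difference (points) | Ratio | Power |
|---|---|---|---|---|---|---|
| 1% | Visit 3 | 0.98% | 2.28% | 1.3 | 2.3 | 10% |
| 1% | Visit 1, 33 days | 2.30% | 4.36% | 2.1 | 1.9 | 17% |
| 1% | Visit 1, 90 days | 4.95% | 7.86% | 2.9 | 1.6 | 21% |
| 2% | Visit 3 | 0.98% | 4.78% | 3.8 | 4.9 | 64% |
| 2% | Visit 1, 33 days | 2.30% | 7.70% | 5.4 | 3.3 | 75% |
| 2% | Visit 1, 90 days | 4.95% | 11.93% | 7.0 | 2.4 | 76% |

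For SD 2% to 4% and mean gains of 1% to 3%, the absolute difference never shrinks. Power can move either way: at SD 4% and a 2% gain it is 77% from Visit 3 and 67% to 74% from Visit 1. Only the risk ratio falls throughout.

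**Step 5: which tables are affected.** Those whose weight baseline is confined to Visits 1 to 3: Study Period III, the combined-period continuous analyses, and galcanezumab-treated time for patients first randomized to galcanezumab. The separate Study Period IV and V baselines include the Visit 7 weight.

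**The case against.** The best defence is that Visit 1 precedes randomization. Drift before dosing is expected to be the same in both arms, so the Study Period III test is not biased. That stands. Weight is also not one of the SAP's safety topics of interest and supports no gated endpoint, and an unscheduled pre-dose weight would be used if one were taken. Those points stand too, though no such weighing is planned.

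Three stronger readings are tempting and should not be drawn.

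- **That the baseline weight precedes any preventive washout.** The protocol says: "Patients are required to discontinue all excluded medications or migraine prevention treatments at least 28 days prior to Visit 2". With a Visit 1 to Visit 2 gap under 28 days, a patient on a preventive must have stopped before Visit 1. Only patients who stop after Visit 1, with a gap of 28 to 45 days, fit that description, and patients on no preventive have no washout. The documents do not say that any preventive alters weight.
- **That the SAP contradicts its own reasoning.** Its stated rationale concerns drugs acting on blood pressure and pulse, with a parallel statement for ECG. It makes no such statement for weight and sets a separate rule. The gap is between that rule and the visit schedule.
- **That a real difference between arms is diluted.** Step 4 of the working shows that the absolute difference does not shrink under the drift model and that power may rise or fall. A flat claim of dilution is not supported.

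It is also fair to object that the drift model has no source in the documents and that zero-mean drift does not shift mean weight change. Both are correct; the rates show scale only.

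**Conclusion.** The point holds as a limited gap in safety measurement. The weight baseline is in practice a screening value taken 33 to 90 days before the first dose, and change in that interval is counted as treatment-emergent. This follows from the schedule alone, for every patient without an unscheduled pre-dose weight.

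In Study Period III the consequence is inflated absolute rates in both arms and added noise, without bias between arms. In galcanezumab-treated time, untreated days make up 27% to 50% of the interval to Visit 7 and 15% to 33% of that to Visit 10 for patients randomized to galcanezumab. Placebo switchers do not share this, so one table mixes two kinds of baseline with no control group to set it against.

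The size of the inflation depends on an assumed variability. At SD 3% per 90 days, the chance of a 7% gain goes from 1.0% to between 2.3% and 5.0% at Visit 7, and from 5.0% to between 6.5% and 8.9% at Visit 10. No primary or key secondary conclusion is touched. Low priority, but cheap to correct.

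**What to change.** **If Visit 3 is still ahead for a useful number of patients:** add weight at Visit 3, before dosing, to the Schedule of Activities. The untreated part of the interval then falls from 33–90 days to zero for a last-value baseline. The existing minimum/maximum rule can also stay: once a Visit 3 value exists, it no longer counts a net pre-dose gain or loss as treatment-emergent. Changing only the SAP rule, with no Visit 3 weight, would alter nothing. The cost is one weighing per patient at an office visit where vital signs are already taken, and a small protocol amendment.

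**If Visit 3 has passed for most patients:** this is likely by the time of the SAP, which was approved in August 2021, about 19 months after the protocol amendment of January 2020. The weighing cannot be recovered, and four changes to the SAP and its outputs would do:

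- State in SAP 6.14.4 and Table CGAX. 6.1 that baseline weight is the screening value for analyses starting at Visit 3.
- Report the distribution of the Visit 1 to Visit 3 interval by arm.
- Rest the interpretation of weight change on the Study Period III comparison between arms.
- Show galcanezumab-treated-time weight separately by original arm.

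These cost some table footnotes and one extra split of an existing table.
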